1.2 Clinical Trials of AR101

Updated information on AR101 clinical trials is provided in the AR101 investigator brochure.

1.2.1 ARC001 Trial

ARC001 was a multicentre, randomized, double-blind, placebo-controlled study of the efficacy and safety of AR101 (characterized peanut allergen) OIT in peanut-allergic children and adults (4 to 26 years of age). The study consisted of a Screening Period, including a Screening DBPCFC, an initial escalation period, an Up-dosing Period, and a Maintenance Period, followed by an Exit DBPCFC.

All eligible subjects underwent a DBPCFC of up to 100 mg (143 mg cumulative) of peanut protein or placebo during the Screening portion of the study. Those subjects who had dose-limiting symptoms (DLS) at or before the 100 mg (143 mg cumulative) challenge dose of peanut protein (measured as 200 mg of peanut flour) were randomized 1:1 to AR101 or placebo.

Subjects received daily oral dosing of AR101 or placebo OIT; all escalation doses occurred in a clinical research center (CRC) or other monitored setting and were administered under direct observation.

After the subjects had been up-dosed to a 300 mg/d dose and had continued to receive that dose for 2 weeks, subjects underwent a DBPCFC of up to 600 mg (1043 mg cumulative) of peanut protein or placebo.

All placebo subjects who completed ARC001 were eligible for rollover into the ARC002 trial. Placebo subjects in ARC002 underwent an escalation and up-dosing schedule identical to that for AR101 subjects in the ARC001 protocol. All subjects on AR101 who passed the DBPCFC by tolerating ≥ 443 mg cumulative of peanut protein with no more than mild symptoms were eligible to proceed to ARC002. Those who did not pass were considered treatment failures.

Efficacy Results:

Fifty-six subjects were randomized: 29 subjects to AR101 and 27 subjects to placebo. Consent for 1 subject was withdrawn after the subject was randomized but before the first dose of study treatment was administered. The intent-to-treat (ITT) population comprised 55 subjects in total, 29 in the AR101 and 26 in the placebo arm. The 2 study groups were overall well matched for baseline characteristics including baseline sensitivity in the Screening DBPCFC. Six subjects in the AR101 arm withdrew from the study prior to the Exit DBPCFC.

For the primary efficacy analysis conducted in the ITT population, AR101 was statistically significantly superior to placebo, with 23 of 29 (79%) AR101 desensitization responders as compared to 5 of 26 (19%) placebo desensitization responders ($p < 0.0001$ by Fisher's exact test).

At the time of the Exit DBPCFC, 100% of the 23 AR101 subjects undergoing the DBPCFC (Completer population) tolerated 443 mg (cumulative) as compared to 5 of the 26 (19%) placebo study completers ($p < 0.0001$ by Fisher's exact test).

At Exit DBPCFC, 18 of 29 (62%) AR101 subjects in the ITT population tolerated 600 mg (1043 mg cumulative) versus none of placebo subjects, resulting in a treatment difference of 62%. Post-hoc analysis by Fisher's exact test yielded statistical significance ($p < 0.0001$). In the Completer population, 18 of 23 (78%) AR101 subjects and no placebo subjects tolerated 600 mg at Exit DBPCFC.

For the key secondary endpoint of the maximum tolerated dose (MTD) with no or mild symptoms at the Exit DBPCFC analyzed using a discrete hazard model, AR101 treatment was shown to increase the probability of tolerating higher maximum doses with no or mild symptoms as compared with placebo treatment. The adjusted probability of tolerating 300 mg was 0.82 for AR101 and 0.14 for placebo; the adjusted probability of tolerating 600 mg was 0.59 for AR101 and 0.01 for placebo. Overall, the treatment effect hazard ratio (95% confidence interval [CI]) was determined to be 0.10 (0.04, 0.25) ($p < 0.0001$), indicating that the risk of failing the Exit DBPCFC in AR101 subjects was one-tenth the risk as compared to placebo subjects.

The percentage of subjects with a maximum symptom severity grade of moderate or severe/worse was lower in the AR101-treated group than in the placebo-treated group at every peanut protein level during the Exit DBPCFC. For AR101 subjects, no subject experienced a severe/worse symptom during Exit DBPCFC, and moderate symptoms were not encountered until a dose of 600 mg was administered. In contrast, at the time of the Exit DBPCFC, at least 1 placebo subject experienced moderate or severe/worse symptoms at each evaluated dose.

For the key secondary endpoint of change from baseline in MTD of peanut protein at Exit DBPCFC analyzed using an analysis of covariance (ANCOVA) model, a treatment difference of $0.912 \log_{10}$ mg ($p < 0.0001$) was observed with a change from baseline in MTD of $1.254 \log_{10}$ mg for AR101 and $0.341 \log_{10}$ mg for placebo. In terms of the ratio of MTD of

peanut protein at the Exit DBPCFC compared to baseline, AR101 subjects were able to tolerate 17.94 times as much peanut protein at the Exit DBPCFC compared to baseline, while placebo subjects were able to tolerate 2.19 times as much peanut protein at the Exit DBPCFC compared to baseline.

For the secondary endpoints of changes in peanut-specific IgE and peanut-specific IgG4 levels and related measures, the relative treatment effect was calculated as a ratio of 2 ratios (study exit result : baseline result in the AR101 group/study exit result : baseline result in the placebo group). The largest relative treatment effect, 4.756, was noted for peanut-specific IgG4, reflecting study exit values that were 5-times baseline in the AR101 group compared to levels that were nearly unchanged in the placebo group. The 95% CI around this relative treatment effect (3.271, 6.915) excluded the null value of 1.

For the secondary endpoint of changes in skin prick test (SPT) results, the difference between treatments was calculated as the change from baseline to study exit in the AR101 group minus the change from baseline to study exit in the placebo group. At the Exit Visit, a notable difference in the change from baseline in maximum peanut SPT wheal diameter was observed between treatment groups, with a treatment difference of -5.2 mm. The 95% CI for this treatment difference (-9.2, -1.1) excluded the null value of 0.

Safety Results:

AR101 was generally well tolerated. The overall incidence of treatment-emergent adverse events (TEAEs) was 97% for the AR101 treatment group and 85% for the placebo group. One subject (3%) in the AR101 group experienced a treatment-emergent serious adverse event (SAE) of anaphylactic reaction related to treatment. One subject (4%) in the placebo group experienced an SAE of presyncope/anaphylaxis related to the peanut protein in the Exit DBPCFC (not investigational product [IP]). An additional subject experienced a pre-randomization, non-treatment-emergent SAE of anaphylactic reaction following the Screening DBPCFC. Four (14%) AR101 subjects discontinued due to adverse events (AEs), with either hypersensitivity (n = 3) or vomiting (n = 1). Two additional AR101 subjects discontinued due to treatment-related reasons that included gastrointestinal (GI) AEs, but not exclusively. No placebo subjects discontinued due to AEs. The most commonly occurring TEAE was hypersensitivity, which was reported in 73% of study subjects. The next most commonly reported TEAEs were pyrexia (16%), upper respiratory tract infection (13%), headache (11%), and vomiting (11%).

Treatment-emergent AEs classified as an allergic reaction by the investigator occurred in 71% of subjects. For these treatment-emergent hypersensitivity events, the Medical Dictionary for Regulatory Activities (MedDRA) coding indicated that the most common preferred terms were vomiting (16%) and abdominal pain (15%). Treatment-emergent hypersensitivity AEs were more common in AR101 subjects than in placebo subjects (90% vs. 50%, respectively); however, these events tended to be mild or moderate in severity and did not typically lead to study withdrawal.

In summary, AR101 was safe, generally well tolerated, and statistically superior to placebo for reducing clinical reactivity to peanut allergen in peanut-allergic children and adolescents

to young adults. AR101 treatment significantly increased the probability of tolerating peanut allergen doses \geq 300 mg and resulted in favorable changes in clinical markers of peanut allergen immunoreactivity, most notably peanut-specific IgG4 levels, as compared to placebo.

1.2.2 ARC003 Study

ARC003 (PALISADE) is an international, multicentre, randomized, double-blind, placebo-controlled study of the efficacy and safety of AR101 in a characterized desensitization OIT regimen in peanut-allergic individuals. The study consists of a Screening phase that includes a Screening DBPCFC, and a double-blind OIT treatment phase that includes an initial escalation period, an Up-dosing Period, and a Maintenance Period, followed by an Exit DBPCFC.

All eligible subjects are randomized in a 3:1 ratio to receive escalating doses of either AR101 or placebo. A DBPCFC will be performed for those subjects achieving the target dose of 300 mg/d and continuing to receive that dose throughout the Maintenance Period (approximately 24 weeks). Subjects who do not reach 300 mg/d will be considered escalation failures and non-responders for the primary analysis. Each subject will be unblinded when he/she completes the DBPCFC at the end of the approximately 24-week Maintenance Period and all major data queries for the subject have been resolved. Those who do not pass the DBPCFC at \geq the 443-mg cumulative challenge dose level will be considered endpoint failures and non-responders for the primary analysis. The study is being monitored by an independent Data Safety Monitoring Committee (DSMC) that has met several times.

1.2.3 ARC004 Study

ARC004 is a randomized, controlled, open-label, multicentre study that will explore alternate dosing interval regimens during extended maintenance with AR101 in subjects completing Study ARC003. The primary objective is to confirm the safety profile of AR101 as measured by the incidence of AEs, including SAEs. The secondary objectives include confirmation of the efficacy of AR101 through reduction in clinical reactivity; evaluation of the efficacy and safety of different AR101 dosing schedules during extended maintenance therapy; evaluation of quality of life and treatment satisfaction during AR101 treatment; and evaluation of the long-term immunologic effects of AR101 treatment. This study is ongoing.

1.2.4 Open-label Follow-on Study, ARC008

The open-label follow-on study ARC008 is designed to accommodate subjects completing Aimmune-sponsored studies with AR101. The study is intended to demonstrate the safety of AR101 for an extended period (months to years) with the following objectives: unblinded expansion of the safety database for AR101, confirmation of the efficacy of OIT with AR101 up-dosed to a maintenance dose of 300 mg/d of peanut protein in the former ARC010 placebo population, and to provide an opportunity to the ARC010 trial participants to maintain the level of desensitization they may have achieved.

1.3 Rationale for Selection of Study Population

This study, ARC010 ARTEMIS, will enroll approximately 160 subjects 4 to 17 years of age with a history of allergy to peanut or peanut-containing foods. The sample size has been selected such that, in combination with the entire clinical experience with AR101 (eg, ARC001, ARC002, ARC003, ARC004), it is sufficient to assess the efficacy of AR101 in the relevant subject populations (Section 9.4).

All subjects enrolled must undergo a Screening DBPCFC to peanut, during which they need to react at or before the 300 mg (444 mg cumulative) dosing level of peanut protein (measured as 600 mg of peanut flour with approximately 50% protein content) in accordance with PRACTALL (Practical Issues in Allergology, Joint United States/European Union Initiative) consensus guidelines (Sampson et al, 2012), regardless of how they were initially diagnosed as peanut allergic. In spite of the change in dose from 100 mg to 300 mg in ARC010, this should continue to select for the more sensitive half of the peanut-allergic population (Remington, 2013; Allen et al, 2014), according to a logistical regression analysis performed by the VITAL 2.0 study groups using food challenge data from multiple sources.

This ARC010 Phase 3 study (ARTEMIS) will focus on the age group most likely to be at greater risk from accidental exposure (ie, 4 to 17 years of age).

The lower age limit of 4 years was selected based on epidemiologic child-developmental considerations related to feeding behavior (Fallon et al, 1984; Cashdan, 1994; Farrow and Blisset, 2012; American Academy of Pediatrics, 2013), as well as practical clinical trial execution considerations and safety.

In the current study, subjects with severe or life-threatening episodes of anaphylaxis or anaphylactic shock will be excluded from enrolling only if they have had such an episode in the 60 days prior to the Screening DBPCFC, but will not otherwise be prohibited from entering the study. This is because peanut-allergic subjects who have had prior life-threatening episodes on exposure to peanut can be considered at high risk for another such episode, and hence, may be considered precisely the type of subjects who could benefit from desensitization therapy. The restriction of 60 days is applied for practical and safety reasons, as subjects who have had such a recent episode may be considered to have a potentially less favorable benefit-risk ratio for undergoing OIT; and such subjects may be reluctant to engage in the study.

1.4 Rationale for Selection of Investigational Product Regimen (Dose and Duration)

For this study, as well as the Phase 3 study ARC003, the dosing regimen used is predicated on the dosing regimen successfully used in the Phase 2 studies, ARC001 and ARC002. The ARC001 dosing regimen, in turn, was built on the work of the Consortium of Food Allergy Research (CoFAR) and its investigators. The basic structure of the dosing regimen consists of a single-day initial escalation at very low doses, followed by a build-up phase of dose escalations, with a single escalation occurring every 2 weeks, and then an maintenance phase at a fixed daily dose. This dosing regimen was shown to be well tolerated and effective in previous studies (Burks et al, 2012) and similarly was shown to be well tolerated and have clinically important activity in the Phase 2 studies ARC001 and ARC002.

The total duration of treatment in the current Phase 3 study will be approximately 9 months (approximately 5 months escalation and 3-4 months maintenance at 300 mg/d). The up-dosing regimen chosen for the current study was selected based on AR101's success in Phase 2.

The duration of maintenance therapy prior to testing for clinical efficacy by DBPCFC in the current study was similarly selected based on the outcome of the Phase 2 study. The clinical trials published to date for peanut OIT have had maintenance periods ranging from 1 to 7 months, and have demonstrated the ability to allow subjects to tolerate challenge doses ranging from 1.25 to 16.7 times their maintenance dose (Clark et al, 2009; Jones et al, 2009; Blumchen et al, 2010; Varshney et al, 2011; Anagnostou et al, 2014; Cronin et al, 2014; Vickery et al, 2016). The data from the ARC001 and ARC002 Phase 2 studies indicate that a clinically meaningful level of desensitization is achieved after up-dosing and just 2 weeks of daily maintenance dosing at 300 mg (with > 95% passing DBPCFC at a cumulative challenge dose of 443 mg of peanut protein and the majority passing at a 1043 mg cumulative challenge) and that extending maintenance dosing from 2 to 14 weeks appears to be associated with some improvement in the overall degree of desensitization. Accordingly, a blinded Maintenance Period of 3 months is considered sufficient to demonstrate efficacy and assess safety in this study. In addition, the ARC003 (PALISADE) Phase 3 confirmatory study will provide evidence of safety and efficacy after 6 months' maintenance therapy; the ARC010 (ARTEMIS) will provide complementary confirmatory evidence at 3 months' duration of maintenance, to evaluate whether clinically relevant desensitization in a significant proportion of subjects occurs at this shorter time frame.

The ability to convey to subjects that they are at a therapeutic level of desensitization in a reasonable timeframe is an important consideration. Thus, the total duration of blinded placebo therapy is limited to a maximum of 56 weeks in this study.

The data from the ARC001 and ARC002 studies, consistent with previously published studies, indicate that the use of a low-dose maintenance phase can provide a clinically meaningful level of desensitization that is considerably higher than the daily maintenance dose. Three studies in particular (Jones et al, 2009; Cronin et al, 2014; Vickery et al, 2016) have specifically reported that daily dosing with 300 mg of peanut protein will allow quantities of peanut protein ranging from 2.1 to 5 grams to be tolerated in an oral food challenge.

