Title	AR101 TRIAL IN EUROPE MEASURING ORAL IMMUNOTHERAPY SUCCESS IN PEANUT ALLERGIC CHILDREN (ARTEMIS)
	available. Subjects who do not tolerate 300 mg peanut protein at the Exit DBPCFC will not continue blinded study treatment in ARC010. The end of the study is defined as the last visit of the last subject. A Data Safety Monitoring Committee (DSMC) will be established to monitor the study for safety.
Study Duration	Each subject will participate in the study for up to approximately 14 months. The expected duration of the study is approximately 18 months.
Primary Endpoint	The primary clinical efficacy endpoint is the proportion of subjects who tolerate at least 1000 mg as a single dose (2043 mg cumulative) of peanut protein with no more than mild symptoms at the Exit DBPCFC.
Secondary Efficacy Endpoints	
Key Secondary Efficacy Endpoints
 
• The proportion of subjects who tolerate at least 600 mg as a single dose (1043 mg cumulative) of peanut protein with no more than mild symptoms at the Exit DBPCFC• The proportion of subjects who tolerate at least 300 mg as a single dose (443 mg cumulative) of peanut protein with no more than mild symptoms at the Exit DBPCFC• The maximum severity of symptoms occurring following ingestion of peanut protein during the Exit DBPCFC 
Other Secondary Efficacy Endpoints
 
• Maximum tolerated dose (MTD) with no more than mild symptoms at Exit DBPCFC• Change from baseline in MTD of peanut protein at Exit DBPCFC• Use of epinephrine as a rescue medication at Exit DBPCFC and comparison to its use at Screening DBPCFC• Changes in serum peanut- and peanut component-specific IgE, total IgE, and peanut-specific IgG4 levels• Changes in peanut skin prick test (SPT) mean wheal diameter• Quality of life assessment using the food allergy quality of life questionnaire (FAQLQ), and the food allergy independent measure (FAIM) questionnaire 
Exploratory Endpoints
 
• Treatment satisfaction assessment using the Treatment Satisfaction Questionnaire for Medication (TSQM-9) and an Exit Questionnaire.• Assessment of palatability (taste and after-taste)

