3.2 Treatment Phase

The Treatment Phase comprises 3 periods:

- **Initial Escalation** (2 consecutive days) – Eligible subjects will be randomized and initiate OIT starting at a dose of 0.5 mg of IP, and then increase the dose incrementally at 20 to 30 minute intervals over the course of a single day to a maximum dose of 6 mg. Subjects who fail to tolerate at least a 3 mg dose will be considered escalation failures and will be discontinued from the study. Subjects who tolerate both the 3 mg and 6 mg doses of IP, or who tolerate the 3 mg but not the 6 mg dose, will undergo confirmatory testing of the tolerability of a 3 mg dose the following consecutive day (refer to Initial Escalation Schedule at end of synopsis). Subjects who tolerate this confirmatory dose will enter the Up-dosing Period. Subjects who do not tolerate this confirmatory dose will be discontinued. Therapy details are found in [Section 3](#) and [Section 6](#) of the protocol.

- **Up-dosing Period** – After the initial escalation period, subjects will report to the CRC every 2 weeks to escalate their OIT dose to an expected daily dose of 300 mg of peanut protein. This constitutes the Up-dosing Period. Subjects will receive daily oral dosing of peanut or placebo OIT for approximately 20 weeks, if up-dosing proceeds without holding at, or reducing, a dose level; up to 40 weeks, maximum. All escalation doses will be administered in a CRC or other monitored setting (unless required by a specific institution, no distinction will be drawn between an investigational site, study center office, clinic, or CRC, provided the capability requirements for monitoring and emergency intervention are met by the facility). All up-dosing activities will be performed under direct observation. Therapy details are found in [Section 3](#) and [Section 6](#) of the protocol.
- **Maintenance Period** – Those subjects who reach the target maintenance dose of 300 mg/d of IP will enter an approximately 12-week Maintenance Period of continued dosing at 300 mg/d, which may be extended by up to an additional 4 weeks (for a maximum Maintenance Period duration of 16 weeks), or to a total Treatment Phase duration of 56 weeks, whichever occurs first.

Treatment will be conducted in a double-blind fashion. The IP (AR101 or placebo) will be coded according to subject randomization number. The subjects and the investigational site personnel will be blinded to treatment assignment.

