3.4 Open-label Follow-on Study – ARC008

All placebo-treated subjects who complete ARC010 are eligible for rollover into the open-label follow-on study ARC008. In ARC008, placebo-treated subjects from ARC010 will undergo an escalation schedule, starting with the 0.5 mg dose and proceeding sequentially through the Up-dosing and Maintenance Periods in an open-label fashion identical to that for subjects who received AR101 in the ARC010 study. If subjects tolerate a daily dose of 300 mg during the Up-dosing Period, they will enter the Initial Maintenance Period. Once 24 weeks in the Initial Maintenance Period have been completed, subjects will then enter the Extended Maintenance Period and receive 300 mg/d until the end of the study. Subjects will be offered optional annual food challenges.

All AR101-treated subjects in ARC010 who pass the DBPCFC at the 443 mg cumulative dose level of peanut protein (ie, tolerate 443 mg cumulative dose with no more than mild symptoms) are eligible to proceed to ARC008. Subjects will receive 300 mg a day for the duration of the study, with visits every 3 months to the CRC. They will be offered the optional annual food challenges. Subjects who do not pass the DBPCFC at the 443 mg cumulative challenge dose level will not be eligible to enroll in ARC008.

If ARC008 is not yet available at the study site, subjects may continue blinded study treatment and have clinic visits every 4 weeks in ARC010 until ARC008 is available. Subjects who do not tolerate 300 mg peanut protein at the Exit DBPCFC will not continue blinded study treatment in ARC010.

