6.5 Exit Visit

Subjects who tolerate 300 mg/d and are maintained at this dose for approximately 12 weeks (up to a maximum of 16 weeks, see [Section 6.11](#)) will return to the clinic for an Exit Visit.

The following procedures will be performed at the Exit Visit:

- Concomitant medication review
- Diet (food allergen) history update
- Completion of the palatability questions before the Exit DBPCFC
- Completion of the FAQLQ and FAIM questionnaires after the completion of the Exit DBPCFC and unblinding of each subject
- Completion of the TSQM-9 and exit questionnaires after the completion of the Exit DBPCFC and unblinding of each subject
- In subjects with asthma: evaluation of asthma severity using the 2007 NHLBI Criteria ([Appendix 2](#)) and the Asthma Control Test questionnaire
- Complete physical examination, including weight and height
- Vital signs (BP, pulse rate, body temperature) taken shortly before the first DBPCFC dose
- PEFR, performed in all subjects 6 years of age or older, measured at approximately the same time for each assessment visit. Three attempts of PEFR should be performed, and the best attempt selected. For subjects 4 or 5 years of age: peak flow rates are to be attempted. The attempt must be documented, and a clinical assessment is required. Airflow assessment should be measured at the same time of day as for prior visit assessments (eg, morning, afternoon, evening).
- Spirometry* (FEV₁), performed when PEFR shows a clinically relevant reduction or the subject shows clinical deterioration (eg, active wheeze on physical examination); 3 attempts of FEV₁ should be performed, and the best attempt selected.

*Only for subjects 6 years of age and older who are able to adequately perform spirometry.

- Urine pregnancy test for females of childbearing potential
- Blood draw (same venipuncture for all samples), prior to DBPCFC, to collect samples for:
 - Peanut- and peanut component-specific IgE, total IgE, and peanut-specific IgG4 assays
 - CBC
 - Optional blood sample for immune cell characterization assays

The amount of blood to be taken for all tests (required immunoglobulin and CBC and optional immune cell characterization assays) will be included in the manual of procedures and not exceed a total volume of 2.5 mL/kg, to a maximum total of 70 mL

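### The 56-week limit on blinded placebo therapy conflicts with a post-challenge continuation that has no stated maximum, and the exit questionnaires wait for the same event

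*Protocol*

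**What the plan says.** **The limit.** Protocol Section 1.4 gives a reason, "The ability to convey to subjects that they are at a therapeutic level of desensitization in a reasonable timeframe is an important consideration", and draws from it that "the total duration of blinded placebo therapy is limited to a maximum of 56 weeks in this study". Other sections use the same number. Section 3.2 limits the Treatment Phase to 56 weeks, Section 6.3.4 requires the Exit DBPCFC by Study Week 56, and Section 6.11 gives 56 weeks as the maximum study duration when maintenance is extended. The synopsis, under Study Duration, says: "Each subject will participate in the study for up to approximately 14 months".

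**The continuation.** Section 3.4 says that, if ARC008 has not yet opened at the site, "subjects may continue blinded study treatment and have clinic visits every 4 weeks in ARC010 until ARC008 is available". The synopsis, Sections 3.3 and 6.5 and Appendix 1 note bb say the same. Subjects who do not tolerate 300 mg at the Exit DBPCFC are excluded from it. None of these places gives a number of weeks or mentions the 56-week limit.

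**Unblinding and questionnaires.** Individual unblinding requires a completed Exit DBPCFC, resolved major queries and ARC008 open at the site (synopsis; Sections 3.3, 4.3.1 and 6.5; Appendix 1 note bb). Section 6.5 lists "Completion of the FAQLQ and FAIM questionnaires after the completion of the Exit DBPCFC and unblinding of each subject" and gives the TSQM-9 and exit questionnaire the same order. The Appendix 1 table places all four at the Exit Visit, 12 to 16 weeks after the first 300 mg/d dose.

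**The concern.** There are two linked problems, and they affect different subjects.

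The first is duration. The limit is worded as a total for blinded placebo therapy, whereas the continuation ends only when another study opens at the site. A site with a subject who reaches Week 56 before ARC008 opens cannot follow both texts.

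The second is the time of assessment. Because the questionnaires follow unblinding and unblinding follows ARC008, the exit quality-of-life value is not taken at one time point across sites. Some subjects would answer after further weeks of treatment, others soon after the challenge. FAQLQ/FAIM is a secondary efficacy endpoint (Section 3.8.1.2) and stands in the hierarchical testing sequence (Section 9.2.2.2), so its timing should be fixed by the plan.

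**Working it through.** **Inputs**
- Up-dosing: "approximately 20 weeks, if up-dosing proceeds without holding at, or reducing, a dose level; up to 40 weeks, maximum" (Section 3.2).
- Maintenance: about 12 weeks, extendable "for a maximum Maintenance Period duration of 16 weeks" (Section 3.2).
- Screening: 28 days, which is 4 weeks (Section 6.11).
- Wait for ARC008 after the Exit DBPCFC: not stated. It is called X below and varied.

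**Step 1: reproduce the limit.** Longest up-dosing + longest maintenance = 40 + 16 = 56 weeks. This equals the Section 1.4 figure, so the number covers time up to the Exit DBPCFC and contains no allowance for the continuation.

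**Step 2: room left at the Exit DBPCFC.**
- Slowest permitted subject: 56 − 56 = 0 weeks.
- On-schedule subject: 20 + 12 = 32 weeks used; 56 − 32 = 24 weeks left.

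**Step 3: add the wait.** Total blinded time = weeks to Exit DBPCFC + X. The values of X are illustrations only.

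| X (weeks) | On schedule, 32 + X | Slowest, 56 + X |
|---|---|---|
| 0 | 32 | 56 |
| 4 | 36 | 60 |
| 12 | 44 | 68 |
| 24 | 56 | 80 |
| 52 | 84 | 108 |

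The slowest subject exceeds 56 weeks for any X above 0, the on-schedule subject for X above 24.

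**Step 4: the participation figure.** 56 weeks + 4 weeks of screening = 60 weeks. At 52.1775/12 = 4.348 weeks per month, 60 / 4.348 = 13.8 months. The stated figure of about 14 months is therefore already used up at the latest permitted Exit DBPCFC.

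**Step 5: who is affected by each part.**
- Continued blinded dosing: only subjects, in either arm, who tolerate 300 mg at the Exit DBPCFC and whose site has not opened ARC008. It is optional.
- Delayed unblinding and questionnaires: as written, every subject with an Exit DBPCFC at such a site, including those who have stopped treatment because they did not tolerate 300 mg. The palatability questions do not wait; Section 6.5 puts them before the challenge.

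**The case against.** The best case for the plan is that the limit concerns the period before the challenge and is loosely worded. It equals 40 + 16 weeks, and Section 1.4 is discussing how long to treat before efficacy is tested. Alternatively, the permissive continuation could be read as sitting under the 56-week maximum study duration in Section 6.11. Either reading is possible, but they lead to different conduct after Week 56 and the text does not choose between them. The Section 1.4 sentence speaks of total duration, so the conflict stands as written.

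Section 6.12 adds that most subjects can infer their assignment from the challenge, which partly serves the purpose of the limit. That does not settle the formal unblinding step to which the questionnaires are tied. It is also fair that unblinding waits for query resolution, so questionnaire timing would vary somewhat even where ARC008 is open.

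Stronger readings are tempting and should be resisted:
- *The limit protects children on placebo.* The stated reason is timely information to subjects about their desensitization.
- *Treatment may go on without end.* No limit is stated, but continuation is optional and ends when ARC008 opens.
- *About 8 of 40 placebo subjects will exceed 56 weeks.* Applying the ARC001 placebo rate at 443 mg of 19% (95% CI 7% to 39%, Section 9.4) gives 0.19 × 40 = 7.6, range 2.8 to 15.6. That estimates who would be eligible to continue. Exceeding 56 weeks also requires a site without ARC008, a choice to continue and a long enough wait. ARC001 also had a lower screening threshold and only 2 weeks at 300 mg before the challenge, so the rate may not carry over.
- *The efficacy result is compromised.* The Exit DBPCFC precedes the continuation.

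**Conclusion.** The contradiction holds. Section 1.4 and the Study Duration text cannot be met together with the continuation text for a subject whose Exit DBPCFC falls at Week 56 and who continues, or for an on-schedule subject who continues for more than 24 weeks. This rests only on the protocol's own durations. How many subjects it would reach cannot be derived, because the protocol gives neither the wait for ARC008 nor the number of sites affected.

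The questionnaire problem holds separately and reaches more subjects: FAQLQ, FAIM, TSQM-9 and the exit questionnaire have a site-dependent time with no stated upper bound. Its effect on the scores cannot be sized from the document. FAQLQ/FAIM is listed last among the other secondary endpoints, which Section 9.2.2.2 calls supportive, and TSQM-9 and the exit questionnaire are exploratory. The primary endpoint, the key secondary endpoints and power are untouched. The point should be corrected, but it does not threaten the main conclusion.

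**What to change.** 1. Reconcile Section 1.4 and the synopsis Study Duration text with the synopsis design text, Sections 3.3, 3.4 and 6.5 and Appendix 1 note bb, so that one statement says whether the 56 weeks includes the continuation. The related statements in Sections 3.2, 6.3.4 and 6.11 should agree with it. Which duration rule is right is for the sponsor and investigators, not this review. The cost is protocol wording.

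2. Tie FAQLQ, FAIM, TSQM-9 and the exit questionnaire to a fixed window at the Exit Visit that does not depend on ARC008. This costs somewhat more than wording: either the questionnaires are no longer completed after unblinding, or the unblinding condition must be separated from ARC008 availability. The first option would have a precedent in the protocol, since Section 6.4 already collects the same questionnaires from early discontinuers, who remain blinded, 14 to 16 days after the last dose. Neither option needs extra subjects or a new procedure.
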